| 8.6 | Sou | irce Documents | 4 |
| 9. Ri: 9.1 | sk Eva Pot | luation | 4 4 |
| 9.2 | Me | thods to Minimize Risk | 4 |
| 9.3 | Stu | dy Site Criteria | 5 |
| 9.4 | Ber | nefits | 5 |
| 9.5 | Risk | k-Benefit Analysis | 6 |
| 10. De 11. St 11.1 | efinitio atistic San | ons3 al Considerations | 6 3 3 |
| 11.2 | Tim | 1 ing | 3 |
| 11.3 | Ana | alysis Sets 4 | 3 |
| 11.4 | Mis | ssing Data4 | 4 |
| 11.5 | End | dpoint Analysis | 4 |
| 12. St 12.1 | udy A Ger | dministration | 4 4 |
| 12.2 | Me | dical Reviewers 4 | 5 |
| 12.3 | Ech | ocardiography Core Laboratory4 | 5 |
| 12.4 | Clin | nical Sites4 | 5 |
| 12.5 | Site | e Training4 | 5 |
| 12.6 | Stu | dy Monitoring4 | 6 |

| 12.7 | Data Collection and Quality Assurance | 47 | | |
|------------------|--|----------|--|--|
| 12.8 | Publication Policy | 48 | | |
| 13. Ethi 13.1 | cal Review and Consideration Confidentiality | 48 48 | | |
| 13.2 | Records and Reports | 48 | | |
| 13.2 | 2.1 Records | 48 | | |
| 13.2 | 2.2 Deviations from Protocol | 49 | | |
| 13.2 | 2.3 Record Retention Policy | 49 | | |
| 14. Fina | ancial and Insurance Considerations | 49 | | |
| 14.1 | Clinical Trial Funding | 49 | | |
| 14.2 | Clinical Trial Insurance | 50 | | |
| 15. Refe | erences | 50 | | |
| Appendi | ix A: Assessments for Stroke and Stroke Severity | A | | |
| Appendi | Appendix B: Frailty IndexB | | | |
| Appendi | Appendix C: 6 Minute Walk TestC | | | |
| Appendi | Appendix D: Clinical Trial Report ContentsD | | | |

1. Study Synopsis

| Title | Safety and Effectiveness of Edwards Lifesciences SAPIEN XT [™] Transcatheter Heart Valve (THV) in the Chinese Population | | |
|--------------------|--|--|--|
| Study Purpose | To evaluate the safety and effectiveness of the SAPIEN XT (Edwards Lifesciences, Irvine, California) transcatheter heart valve implantation (TAVI) in Chinese patients with symptomatic severe calcific aortic stenosis who are considered at high risk for surgical valve replacement. | | |
| Study Design | Prospective, single-arm, multi-center study. The study is expected to take 5.5 years to complete. | | |
| Study Device | Edwards SAPIEN XT [™] Transcatheter Heart Valve and NovaFlex+ delivery system | | |
| Study Population | A maximum of 60 patients with symptomatic severe calcific aortic stenosis requiring transcatheter aortic valve implantation (TAVI), who are considered high risk for surgical valve replacement who receive a SAPIEN XT THV. | | |
| Inclusion Criteria | Subjects who are considered to be operable and high risk for surgical valve replacement: 8 ≤ STS Score ≤ 15 or 15 ≤ Logistic EuroSCORE ≤ 40. If STS score is below 8 and/or Logistic EuroSCORE is below 15, patients should have other clinical or anatomical risk factors that would be considered high risk for surgery and documented by the heart team Severe symptomatic aortic stenosis requiring aortic valve replacement characterized by one or more of the following within 60 days prior to the index procedure: AVA < 0.8 cm², Indexed AVA <0.5 cm²/m², mean gradient > 40mmHg, or peak aortic jet velocity > 4.0m/sec. [41] NYHA Functional Class II or greater. The study patient or the study patient's legal representative has been informed of the nature of the study, agrees to its provisions and has provided written informed consent as approved by the EC of the respective clinical site. The study patient agrees to comply with all required post- procedure follow-up visits. Native aortic valve annulus area between 314 mm² - 660 mm² as measured by CT. | | |

| | 7. Native aortic annulus diameter between 20 mm – 29 mm as measured by CT. | | | |
|--------------------|--|--|--|--|
| Exclusion Criteria | measured by CT. 1. Evidence of an acute myocardial infarction ≤ 1 month (30 days) before the intended treatment [(defined as: Q wave MI, or non-Q wave MI with total CK elevation of CK-MB ≥ twice normal in the presence of MB elevation and/or troponin level elevation (WHO definition)]. 2. Aortic valve is a congenital unicuspid or is non-calcified. 3. Aortic valve is bicuspid and the patient is less than 60 years old, or the aortic valve is bicuspid with no raphe (Sievers classification type 0) [42] 4. Anomalous coronary artery that would interfere with proper placement of the valve. 5. Mixed aortic valve disease (aortic stenosis and aortic | | | |
| | regurgitation with predominant aortic regurgitation >3+). 6. Pre-existing mechanical or bioprosthetic valve in any position. 7. Any therapeutic invasive cardiac procedure resulting in a | | | |
| | permanent implant that is performed within 30 days of the index procedure. Implantation of a permanent pacemaker or ICD is not considered exclusion criteria. | | | |
| | after a qualifying echocardiogram). | | | |
| | Leukopenia (WBC < 3000 cell/mL), acute anemia (Hgb < 9 g/dL), Thrombocytopenia (Plt < 50,000 cell/mL). Renal insufficiency (creatinine > 3.0 mg/dL) and/or renal | | | |
| | replacement therapy at the time of screening. 11. Untreated clinically significant coronary artery disease requiring revascularization. | | | |
| | 12. Emergency interventional/surgical procedures within one month (30 days) prior to the TAVI procedure. | | | |
| | 13. Hypertrophic cardiomyopathy with or without obstruction (HOCM). | | | |
| | 14. Severe ventricular dysfunction with LVEF < 20%. | | | |
| | thrombus or vegetation. | | | |
| | 16. Active upper GI bleeding within 3 months (90 days) prior to procedure. | | | |
| | 17. A known contraindication or hypersensitivity to all anticoagulation regimens, or inability to be anticoagulated for the study procedure. | | | |

| | Stroke or transient ischemic attack (TIA) within 3 months (90 days) of the procedure. Estimated life expectancy < 12 months (365 days) due to carcinomas, chronic liver disease, chronic renal disease or chronic end stage pulmonary disease. Significant aortic disease, including marked tortuosity (hyperacute bend), aortic arch atheroma [especially if thick (> 5 mm), protruding or ulcerated] or narrowing (especially with calcification and surface irregularities) of the abdominal or thoracic aorta, severe "unfolding" and tortuosity of the thoracic aorta. Iliofemoral vessel characteristics that would preclude safe placement of the introducer sheath. Currently participating in an investigational drug or another device study. Note: Trials requiring extended follow-up for products that were investigational, but have since become commercially available, are not considered investigational trials. Active bacterial endocarditis within 6 months (180 days) of procedure, with our without treatment. |
|---------------------|--|
| Primary Endpoint | All-cause mortality at 30 days |
| Secondary Endpoints | Safety Cardiovascular mortality at 30 days Stroke at 30 days TIA at 30 days All-cause mortality & stroke at 30 days Vascular complications (major) at 30 days Bleeding complications (life threatening or disabling, and major) at 30 days Myocardial infarction at 30 days Acute kidney injury at 30 days (stages II and III) Coronary obstruction requiring intervention at 30 days Permanent pacemaker implantation at 30 days Device Success Absence of procedural mortality AND Correct positioning of a single prosthetic heart valve into the proper anatomic location AND Intended performance of the prosthetic heart valve (no prosthesis-patient mismatch and mean aortic valve |

| | gradient <20mmHg or peak velocity <3m/s, AND no |
|----------------------------|---|
| | moderate or severe prosthetic valve regurgitation) at 30 |
| | Davs |
| | |
| | Efficacy |
| | New York Heart Association (NYHA) Classification at 30 |
| | days |
| | Hemodynamic valve performance evaluation by |
| | echocardiography for aortic valve stenosis and aortic |
| | valve regurgitation (paravalvular & central) at 30 Days |
| | as determined by Echo core lab |
| | |
| Patient Follow-up Schedule | Patients consented to trial and implanted with a SAPIEN XT |
| | THV will be assessed at Baseline, Peri- and Post-Procedure, |
| | Index Hospitalisation Discharge, and 30 Days, 6 Months, 1 |
| | Year, 2 Years, 3 Years, 4 Years and 5 Years post-procedure. |
| Study Duration | Subjects implanted with SAPIEN XT THV will be followed for 5 |
| | years after the procedure |
| Statistical Considerations | The sample size of 50-60 patients is determined per Chinese |
| | regulatory requirements and agreement for a regional study of |
| | a medical device already approved in other regions based on a |
| | well-designed prospective study. |
| Sponsor | Edwards Lifesciences LLC |
| | [name] |
| | [name] |
| Local Sponsor | Edwards (Shanghai) Medical Products Co. Ltd |
| | |
| | |
| Sponsor Representative / | |
| Study Manager | THV Clinical Project Manager |
| | Edwards Lifesciences Pty Ltd |
| | |
| | |
| Principal Investigator | [name] [name] |
| | Fuwai Hospital |
| | |

| | Beijing, China | | |
|--------------------|---|--|--|
| Study Centers | Fuwai Hospital, CAMS&PUMC | | |
| | Beijing, China | | |
| | | | |
| | [name] [name] | | |
| | WestChina Hospital, Sichuan University | | |
| | Chengdu, China | | |
| | [name] [name] | | |
| | The Second Affiliated Hospital of Zhejiang University School of | | |
| | Medicine | | |
| | Hangzhou, China | | |
| Contract Research | | | |
| Organization (CRO) | | | |
| | | | |
| | | | |

2. Introduction

2.1 Study Purpose

The purpose of this trial is to evaluate the safety and effectiveness of the SAPIEN XT transcatheter heart valve implantation (TAVI) in Chinese patients with symptomatic severe calcific aortic stenosis who are considered at high risk for surgical valve replacement. Clinical data will be submitted for the purposes of obtaining Chinese regulatory approval.

2.2 Clinical Background

Prolonged average life expectancy has resulted in an aging population and consequently, an increase in the number of patients with acquired, calcific, severe, symptomatic aortic stenosis (AS). The standard of care therapy for patients suffering from severe AS is aortic valve replacement surgery (AVR). In the aged population, many patients are too sick to be operated or have co-morbidities that preclude the option for surgery [1].

AS is a progressive, debilitating and life-threatening disease if left untreated. Affected individuals are typically > 65 years of age. The pathology involves progressive calcification of the leaflet bodies which limits normal cusp opening during systole. Cellular aging and degeneration have been implicated in this form of the disease and diabetes mellitus and hypercholesterolemia are risk factors.

2.2.1 Disease Process

The pathophysiology of AS includes an increase in afterload, progressive hypertrophy of the left ventricle, and a decrease in systemic and coronary blood flow as consequences of valve obstruction. Typically, patients with AS are free from cardiovascular symptoms (e.g. angina, syncope and/or heart failure) until late in the course of the disease. However, once symptoms manifest, the prognosis is poor, especially when associated with congestive heart failure. Death in general, including sudden death, occurs primarily in symptomatic patients. Survival analyses have demonstrated that the interval from onset of symptoms to time of death is approximately two years in patients with heart failure, three years in those with syncope, and five years in those with angina [2]. Among symptomatic patients with moderate-to-severe AS treated medically, mortality rates after the onset of symptoms were approximately 25% at 1 year and 50% at 2 years and more than 50% of deaths were sudden [3].

Grading the severity of AS is based on a variety of hemodynamic and natural history data. According to the ACC/AHA guideline authors, AS is best described as a continuum. In patients with moderate-to-severe AS, valve area may decline up to 0.3 cm² per year and the systolic pressure gradient across the valve can increase by as much as 15-19 mmHg per year, with a higher rate of progression observed in elderly patients with coronary artery disease (CAD) and chronic renal insufficiency [4]. Relief of aortic valve obstruction typically results in an improvement of symptoms, hemodynamic parameters, and global left ventricle systolic function, as well as reversal of left ventricular hypertrophy [4,5].

2.2.2 Alternative Therapies/Techniques

Treatment options for patients suffering from symptomatic AS include palliation of symptoms without valve replacement (non-surgical standard therapy), surgical aortic valve replacement (AVR) or TAVI with another valve. Treatment options are determined by patient risk for morbidity or mortality after surgery and patient choice. Non-surgical treatment options including balloon aortic valvuloplasty have been demonstrated to lead to shortened life expectancies and poor quality of life [6-8]. Patients considered poor candidates for AVR typically present with significant morbidities or anatomic limitations, such as severely calcified aorta, chest wall radiation, etc. [9]. Also a state of frailty may lead to a patient or physician decision to forego surgery. AVR has been demonstrated to have excellent long term outcomes for patients with aortic valve stenosis, including patients who were operable but had predicted high risk for surgery (by STS PROM > 10) [10-15].

Transcatheter aortic valve implantation (TAVI) was first performed in man in 2002 and was followed by European commercialization in 2007 [16-18]. Today more than 160,000 patients worldwide have undergone TAVI and there is a proliferation of published literature supporting

the safety and performance of the SAPIEN balloon expandable heart valve (SAPIEN, SAPIEN XT, and SAPIEN 3). The Edwards THV clinical research program includes more than 15,000 patients enrolled in approximately 23 clinical studies which include first-in-man, feasibility, pivotal randomized controlled trials and post-market registries. Results from these trials have been publicly reported in the scientific congresses and journals [19-34].

The PARTNER (I) trial was the first of its kind to randomize patients to THV versus the current standard of care, and has produced the most conclusive evidence of the safety and effectiveness of the Edwards SAPIEN THV in both high risk surgical (Cohort A) and inoperable patients with symptomatic aortic stenosis (Cohort B). Cohort B randomized patients between medical therapy and transfemoral (TF) TAVI. The one-year results for survival and functional improvements in both New York Heart Association (NYHA) class and Quality of Life indices indicated that TAVI should be the new standard of treatment for patients with severe AS considered to be at too high a risk to undergo surgical AVR [24, 35]. Recent results support the sustained benefit up to five years post TAVI [19, 21, 36].

The Cohort A randomized TAVI to AVR in patients who were considered at high operative risk for surgery based on the STS score [37]. While peri-procedural stroke rates were higher in the TAVI arm (3.8% vs. 2.1% [p=0.20]), the overall composite endpoint of all-cause mortality or stroke at 1 year was not different between the two arms (24.2% for TAVI vs. 26.8% for AVR (difference -2.6%, 95% upper confidence limit 3.0%, pre-defined margin 7.5%; p = 0.001 for non-inferiority). Moreover, despite the initial higher 30-day stroke rate in the TAVI arm, the mortality at 30 days was numerically lower in the TAVI arm (3.4% vs. 6.5% for TAVI and AVR, respectively). This difference did not reach statistical significance, however (p=0.07). Major vascular complications were more frequent after TAVI (11.0% vs. 3.2%, P<0.001), whereas major bleeding (9.3% vs. 19.5%, P<0.001) and new-onset atrial fibrillation (8.6% vs. 16.0%, P<0.001) were more frequent after AVR. Both NYHA Class and Quality of Life index improvements favoured TAVI at 30 days, but were similar after 1 year. Paravalvular aortic regurgitation (PAR) was more frequent after TAVI than AVR (P<0.001), and a late association between residual PAR and mortality has been subsequently revealed [21].

Three year data demonstrate sustained benefits for aortic valve replacement in both the TAVI and AVR arms with the SAPIEN valve demonstrating a sustained durability similar to surgical bioprostheses with no differences in long term mortality (44.2 vs. 44.8%, for TAVI vs. AVR, respectively)[38].

Conclusions from the first randomized Edwards SAPIEN THV studies indicate that balloon expandable TAVI should be recognized as the standard of care for inoperable patients and is an

acceptable alternative to AVR in high risk patients. Also reported were significant outcomes related to the study device versus standard therapy control, such as stroke, major vascular complications and major bleeding events which had significant impact on overall mortality. These findings were consistent with earlier published reports. Despite the high-risk nature of the population studied, it is a widely held belief that design improvements in the profile and ease of use of the delivery system may reduce procedure-related adverse events and thus support expansion of the study population to include patients previously excluded due to anatomical limitations. Two year data from the SOURCE XT post-approval study of the SAPIEN XT demonstrate similar long-term performance to the SAPIEN valve [39], with more favourable long-term survival for patients presenting with few comorbidities at baseline. The SAPIEN 3 is the most recent SAPIEN THV to obtain the CE Mark (January 2014). The SAPIEN 3 has been designed to be placed via a fully percutaneous TF approach using the Edwards Expandable Sheath ("eSheath"), and its TF delivery has demonstrated the lowest rates of death, stroke, and major vascular complications (2.1, 1.0 and 4.2%, respectively) for any SAPIEN THV [40]. The robust body of consistently improving clinical evidence presented by Edwards SAPIEN transcatheter valve platforms attests to the Edwards history of leadership in heart valve bioprosthesis technology.

3. Study Device

3.1 SAPIEN XT Transcatheter Heart Valve

The Edwards SAPIEN XT Transcatheter Heart Valve (Figure 1) is indicated for use in patients with severe, symptomatic, calcified aortic stenosis.

The Edwards SAPIEN XT transcatheter heart valve (THV) is comprised of a balloon-expandable, radiopaque, nickel cobalt chromium frame, trileaflet bovine pericardial tissue valve, and polyethylene terephthalate (PET) fabric skirt. It is treated according to the Edwards ThermaFix process, and is packaged and terminally sterilized in glutaraldehyde.

Figure 1 SAPIEN XT Transcatheter Heart Valve (THV)

23mm and 26mm SAPIEN XT THV

29mm SAPIEN XT THV

The THV is intended to be implanted in a native annulus size range comparable to the following measurements:

| Nativo Valvo | Native Valve A | | |
|----------------------|-------------------------|--------------|----------|
| | Area | Area Derived | THV size |
| Allitulus Size (TEE) | | Diameter | |
| 18-22mm | 314-415 mm ² | 20-23 mm | 23 mm |
| 21-25mm | 415-530 mm ² | 23-26 mm | 26 mm |
| 24-27mm | 530-660 mm ² | 26-29 mm | 29 mm |

Table 1 SAPIEN XT Annulus and Valve Sizing

3.1.1 NovaFlex+ Delivery System

The NovaFlex+ delivery system includes a handle that provides a Flex Wheel for articulation of the Flex Catheter, a tapered tip at the distal end of the delivery system to facilitate crossing the native valve, and a Balloon Catheter for deployment of the THV. The handle contains a Flex Indicator that shows whether or not the Flex Catheter is articulated, a Valve Alignment Wheel for fine adjustment of the THV during Valve Alignment, a Press/Release Button that enables movement between handle positions, and a flush port to flush the Flex Catheter. A stylet is included within the guidewire lumen of the delivery system. The Balloon Catheter has radiopaque Valve Alignment Markers defining the Valve Alignment Position and the working length of the balloon. A radiopaque Double Marker proximal to the balloon indicates the Flex Catheter position during deployment.

| Fable 2 | SAPIEN XT | THV | NovaFlex+ | Kit |
|---------|-----------|-----|-----------|-----|
|---------|-----------|-----|-----------|-----|

| Product Name | 23mm System (9355NF23) | 26mm System (9355NF26) | 29mm System (9355NF29) | | |
|--|---------------------------|---------------------------|---------------------------|--|--|
| | Model/REF | | | | |
| NovaFlex+ Kit, compromised of the following: | | | | | |

| Edwards SAPIEN XT Transcatheter Heart Valve | 9300TFX (23mm) | 9300TFX (26mm) | 9300TFX (29mm) | | |
|---|-------------------|-------------------|-------------------|--|--|
| NovaFlex+ Delivery System ¹ | 9355FS23 | 9355FS26 | 9355FS29 | | |
| Edwards Expandable Introducer Sheath Set ("eSheath") | 916ES23 | 918ES26 | 920ES29 | | |
| RetroFlex Dilator Kit | 9100DKS | | | | |
| Edwards Transfemoral Balloon Catheter | 9350BC20 | 9350BC23 | 9350BC25 | | |
| Crimper | 9350CR | | | | |
| Inflation Devices (x2) | | | | | |
| ¹ Includes the Qualcrimp Crimping Accessory, and 2-piece Crimp Stopper | | | | | |

3.1.2 Expandable Introducer Sheath Set

The Edwards eSheath Introducer Set is intended for introduction of interventional devices in the vascular system. The product is intended for use by physicians trained and experienced in interventional techniques. Standard techniques for placement of vascular access sheaths should be employed.

3.1.3 Edwards Transfemoral Balloon Catheter

The balloon catheter is indicated for dilation of stenotic native aortic valve leaflets.

3.1.4 RetroFlex Dilator Kit

The RetroFlex dilator kit contains a set of four hydrophilically coated tapered dilators used for arterial dilatation.

3.1.5 Crimper

The crimper reduces the diameter of the THV to mount it to the delivery system. The crimper is comprised of a compression mechanism that is closed with a handle located on the housing. The crimper includes a 2-piece Crimp Stopper (packaged with the delivery system) used to correctly crimp the THV.

3.1.6 Qualcrimp

The Qualcrimp crimping accessory (packaged with the NovaFlex+ delivery system) is used during crimping of the THV.

3.1.7 Inflation Devices

Inflation devices with a locking mechanism are used during native valve predilation and THV deployment.

3.2 Instructions for Use (IFU)

These devices must always be used according to the current IFU provided with each product

4. Study Objective

The objective of the study is to evaluate the safety and effectiveness of the SAPIEN XT transcatheter heart value implantation in Chinese patients with symptomatic severe calcific aortic stenosis who are considered at high risk for surgical value replacement.

4.1 Primary Endpoint

The primary endpoint is all-cause mortality at 30 days post-index procedure.

4.2 Secondary Endpoints

Safety

- Cardiovascular mortality at 30 days
- Stroke at 30 days
- TIA at 30 days
- All-cause mortality & stroke at 30 days
- Vascular complications (major) at 30 days
- Bleeding complications (life threatening or disabling, and major) at 30 days
- Myocardial infarction at 30 days
- Acute kidney injury at 30 days (stages II and III)
- Coronary obstruction requiring intervention at 30 days
- Permanent pacemaker implantation at 30 days

Device Success

- Absence of procedural mortality AND
- Correct positioning of a single prosthetic heart valve into the proper anatomic location AND
- Intended performance of the prosthetic heart valve (no prosthesis-patient mismatch and mean aortic valve gradient <20mmHg or peak velocity <3m/s, AND no moderate or severe prosthetic valve regurgitation) at 30 Days

Efficacy

- New York Heart Association (NYHA) Classification at 30 days
- Hemodynamic valve performance evaluation by echocardiography for aortic valve stenosis and aortic valve regurgitation (paravalvular & central) at 30 Days as determined by Echo core lab

5. Patient Population

To ensure that a minimum of 50 patients are implanted with the SAPIEN XT THV and complete the 30 Day follow-up for Primary Endpoint, up to 60 patients will be enrolled and implanted with SAPIEN XT THV. Each site may not contribute more than 30 implanted patients to the study population. All patients will be followed for 5 years.

Enrolment will be closely monitored to ensure not more than 60 patients are implanted with SAPIEN XT THV.

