5.2 Exclusion Criteria

Patients must not meet any of the Exclusion Criteria in order participate in the study

- Evidence of an acute myocardial infarction ≤ 1 month (30 days) before the intended treatment [(defined as: Q wave MI, or non-Q wave MI with total CK elevation of CK-MB ≥ twice normal in the presence of MB elevation and/or troponin level elevation (WHO definition)].
- 2. Aortic valve is a congenital unicuspid or is non-calcified.
- 3. Aortic valve is bicuspid and the patient is less than 60 years old, or the aortic valve is bicuspid with no raphe (Sievers classification type 0) [42]
- 4. Anomalous coronary artery that would interfere with proper placement of the valve.
- 5. Mixed aortic valve disease (aortic stenosis and aortic regurgitation with predominant aortic regurgitation >3+).

- 6. Pre-existing mechanical or bioprosthetic valve in any position.
- 7. Any therapeutic invasive cardiac procedure resulting in a permanent implant that is performed within 30 days of the index procedure. Implantation of a permanent pacemaker or ICD is not considered exclusion criteria.
- 8. Any patient with a balloon valvuloplasty (BAV) within 30 days of the procedure (unless BAV is a bridge to procedure after a qualifying echocardiogram).
- Leukopenia (WBC < 3000 cell/mL), acute anemia (Hgb < 9 g/dL), Thrombocytopenia (Plt < 50,000 cell/mL).
- 10. Renal insufficiency (creatinine > 3.0 mg/dL) and/or renal replacement therapy at the time of screening.
- 11. Untreated clinically significant coronary artery disease requiring revascularization.
- 12. Emergency interventional/surgical procedures within one month (30 days) prior to the TAVI procedure.
- 13. Hypertrophic cardiomyopathy with or without obstruction (HOCM).
- 14. Severe ventricular dysfunction with LVEF < 20%.
- 15. Echocardiographic evidence of intracardiac mass, thrombus or vegetation.
- 16. Active upper GI bleeding within 3 months (90 days) prior to procedure.
- 17. A known contraindication or hypersensitivity to all anticoagulation regimens, or inability to be anticoagulated for the study procedure.
- 18. Stroke or transient ischemic attack (TIA) within 3 months (90 days) of the procedure.
- 19. Estimated life expectancy < 12 months (365 days) due to carcinomas, chronic liver disease, chronic renal disease or chronic end stage pulmonary disease.

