| Conduction Disturbances and Arrhythmias | Up to 72 h, continuous rhythm monitoring is recommended in order to maximize detection of arrhythmias Data elements to be collected should include: Baseline conduction abnormalities, paroxysmal or permanent atrial fibrillation (or flutter), and presence of permanent pacemaker* Implant-related new or worsened cardiac conduction disturbance (new or worsened first degree atrioventricular (AV) block, second degree AV block (Mobitz I or Mobitz II), third degree AV block, incomplete right bundle branch block, right bundle branch block, intraventricular conduction delay, left bundle branch block, including block requiring permanent pacemaker implant Persistent or transient high degree AV block. High grade AV block is persistent if it is present every time the underlying rhythm is checked New permanent pacemaker implantation, with precision of the indication and number of days post-implant of placement of new permanent pacemaker New-onset atrial fibrillation (or flutter)[†] Any new arrhythmia resulting in hemodynamic instability or requiring therapy. | VARC-2 |

| Term | Definition | Reference/ |
|-----------------------------|---|---------------|
| | | Justification |
| | * Type of permanent pacemaker should be recorded (e.g. defibrillator, | |
| | single versus dual chamber, biventricular) | |
| | within bespitalization that has the ECC characteristics of strial fibrillation | |
| | (or flutter) and lasts sufficiently long to be recorded on a 12 load ECC, or at | |
| | (of fuller) and lasts sufficiently long to be recorded on a 12-lead ECG, of at | |
| | t Therapy includes electrical/medical cardioversion or initiation of a new | |
| | medication (oral anticoagulation, rbythm or rate controlling therapy) | |
| Conversion to Open Surgery | Conversion to open stornetomy during the TAVI procedure secondary to | |
| (TAVI-related) | any procedure-related complications | VARC-2 |
| Coronary obstruction (TAVI- | Angiographic or echocardiographic evidence of a new partial or complete | VARC-2 |
| related) | obstruction of a coronary ostium either by the valve prosthesis itself the | VANC 2 |
| | native leaflets, calcifications, or dissection, occurring during or after the | |
| | TAVI procedure | |
| Device Malfunction | The failure of a device to meet any of its performance specifications or | ISO14155:2011 |
| | otherwise perform as intended. Performance specifications include all | |

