11.3 Analysis Sets

- As Treated (AT) Population: all patients that were enrolled in the trial for whom the SAPIEN XT valve implant procedure was begun, defined as the time in which the first Edwards' investigational device is inserted into the patient.
- *Valve Implant (VI) Population:* all AT patient who received and retained the SAPIEN XT valve upon leaving the procedure room

All patients documented as part of the roll-in patient strategy will not be included in analysis population and evaluated separately.

The primary and secondary endpoints will be reported based on the AT Population. AT patients that did not receive the SAPIEN XT valve will be censored at 30 days or at resolution of any AE.

Descriptive and summary statistical analysis will be performed on all endpoints. Patient listings for adverse events, deaths, and reinterventions will include all enrolled patients.

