11.5 Endpoint Analysis

Patient data listings and tabular and graphical presentations of results will be provided. All clinically relevant baseline and follow-up variables will be tabulated. Descriptive statistics will be used for continuous variables (e.g., mean, standard deviation, sample size, minimum, and maximum) and frequency tables or proportions for discrete variables.

Kaplan Meier estimates will be performed at the pre-specified follow-up times to project the estimates for time-related safety endpoints. The Kaplan-Meier analysis will be used to compute the 30-day mortality rate, the primary endpoint; the standard error and confidence limits will be computed using Greenwood's algorithm.

Echocardiographic data will be analyzed by an Echo core laboratory with respect to the degree of total aortic valve regurgitation (TVR) and paravalvular aortic valve regurgitation (PAR) according to the VARC-2 definitions [46].

These data and other categorical data (e.g., NYHA class) will also be presented as shift from baseline for each of the pre-specified follow-up periods.

More specific information regarding the statistical analysis will be presented in the Statistical Analysis Plan (SAP).

12. Study Administration

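### Read as the risk of new pacemaker implantation, the 30-day rate on all As Treated patients is too low by the share already paced at baseline; report it among unpaced patients as well

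*Combined protocol and SAP*

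**What the plan says.** - Section 4.2 names the endpoint as "Permanent pacemaker implantation at 30 days". The label does not say new, and it sets no condition on pacemaker status at baseline.
- Section 11.3 gives one rule for all endpoints: "The primary and secondary endpoints will be reported based on the AT Population". The AT set is "all patients that were enrolled in the trial for whom the SAPIEN XT valve implant procedure was begun", with the start defined by insertion of the first investigational device. Baseline pacemaker status plays no part.
- Section 5.2, exclusion 7, bars recent permanent cardiac implants and then makes an exception: "Implantation of a permanent pacemaker or ICD is not considered exclusion criteria". No other criterion excludes a patient for having a pacemaker, whenever it was placed.
- Section 10, under conduction disturbances and arrhythmias, lists among the data elements "Baseline conduction abnormalities, paroxysmal or permanent atrial fibrillation (or flutter), and presence of permanent pacemaker". In the same entry it describes the event as "New permanent pacemaker implantation, with precision of the indication and number of days post-implant of placement of new permanent pacemaker".
- Section 11.5 covers estimation: "Kaplan Meier estimates will be performed at the pre-specified follow-up times to project the estimates for time-related safety endpoints". It states no restriction of the risk set and leaves further detail to a SAP.

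**The concern.** The event that section 10 describes can happen only to a patient who is not yet paced. The analysis rule in section 11.3 nevertheless divides by everyone treated. If some treated patients arrive with a pacemaker, the reported figure mixes the risk of new implantation with the share of patients who could not have one.

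This is a single-arm study whose data will be submitted for Chinese regulatory approval (section 2.1). There is no control arm to share the dilution, so the absolute rate is the result. Two series with the same risk for an unpaced patient would report different rates if their baseline pacemaker prevalence differed. The direction favours the device.

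**Working it through.** **Inputs.** The sample size is 50 to 60 (section 11.1). The protocol states no expected pacemaker rate and no baseline prevalence, so there is no figure of its own to reproduce. The event counts (6 in 60, 5 in 50) and the prevalences (5%, 10%, 20%) are assumptions. Taking N = 60 for the AT set is also a simplification: the limit of 60 counts patients who leave the procedure room with the valve (section 6.3.2), whereas the AT set also includes those in whom a device was inserted but the valve was not retained.

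**Formulas.** Let x be new implantations, N the AT patients, and m those paced at baseline.

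- All-AT rate = x / N
- At-risk rate = x / (N − m)
- Hence all-AT rate = at-risk rate × (1 − m/N)

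The relative shortfall is m/N, the baseline prevalence, whatever the event rate.

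**Results for N = 60, x = 6**, with exact (Clopper-Pearson) 95% intervals:

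| Assumed prevalence | m | Rate | 95% CI |
|---|---|---|---|
| All AT | – | 6/60 = 10.0% | 3.8 to 20.5 |
| 5% | 3 | 6/57 = 10.5% | 4.0 to 21.5 |
| 10% | 6 | 6/54 = 11.1% | 4.2 to 22.6 |
| 20% | 12 | 6/48 = 12.5% | 4.7 to 25.2 |

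The shift is 0.5 to 2.5 percentage points. For N = 50 and x = 5, the all-AT rate is 10.0% (3.3 to 21.8). The at-risk rate is 5/45 = 11.1% at 10% prevalence and 5/40 = 12.5% at 20%.

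**Other direction.** If the true at-risk rate were 20%, the all-AT rate would be 20% × 0.95 = 19.0%, 20% × 0.90 = 18.0% or 20% × 0.80 = 16.0% at the same three prevalences.

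**Will it arise?** The chance of at least one paced patient is 1 − (1 − prevalence)^N. At 3% prevalence this is 84% for N = 60 and 78% for N = 50. At 5% it is 95% and 92%, and at 10% it is above 99% for both.

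**Does Kaplan-Meier remove the problem?** No. Without censoring, one minus the Kaplan-Meier estimate with all AT patients in the risk set is x/N, the same diluted figure. It becomes x/(N − m) only if patients paced at baseline are left out of the risk set.

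**The case against.** Several points on the other side have weight.

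- **All-AT incidence is legitimate.** New implantations divided by all treated patients describes what happened in the treated group. A reader might infer that the planned rate is simply biased. The protocol does not support that: it never says it targets the risk in unpaced patients, and the figure is low only if read that way. This stands, and it is why the all-AT rate should be kept and labelled rather than replaced.
- **A pacemaker placed shortly before the procedure.** A reader might also infer that leaving such a pacemaker out of the event count is a fault. It is not. Adverse event collection begins when anesthesia is first given (section 8.1 and footnote 1 to the visit schedule), so a pre-procedure implant is correctly not an event. Exclusion 12, on emergency procedures in the preceding 30 days, may keep some of these patients out altogether. The only issue is the denominator.
- **Section 10 already says new.** The event is described correctly there, and baseline status is listed as something that should be collected. This narrows the point to the denominator and to the short label in section 4.2. That label, read alone, leaves open whether a change or upgrade of an existing system counts.
- **The SAP could set an at-risk denominator.** Section 11.5 leaves room for it. The text available does not do so, and the general rule in section 11.3 points to all AT patients.
- **Readers could work it out.** Section 11.5 promises tabulation of clinically relevant baseline variables and patient listings, so the at-risk rate could probably be reconstructed. That reduces the harm, but the reported rate would still be the diluted one.
- **The effect is small.** It is, and the endpoint is descriptive, with no hypothesis or margin.

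**Conclusion.** The point holds as a modest reporting improvement. Under the stated rule, the pacemaker rate equals the risk among unpaced patients multiplied by one minus the baseline pacemaker prevalence. The direction is certain once one AT patient is paced at baseline and the event is new implantation, as in section 10. The size is not known from the protocol. Under the assumed 6 events in 60 and a prevalence of 5% to 20%, it is 0.5 to 2.5 points on a rate of 10.0%, well inside the sampling uncertainty of about 4% to 21%. The primary endpoint is unaffected and no decision rule changes. The case for acting is that the absolute rate is the result in a single-arm regulatory study, and that the correction needs no data beyond what section 10 already lists.

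**What to change.** 1. In section 4.2 and the synopsis, word the endpoint as new permanent pacemaker implantation within 30 days, to match section 10.
2. In section 11.3 or the SAP, report it among AT patients without a pacemaker at baseline. For Kaplan-Meier, restrict the risk set in the same way.
3. Show the all-AT rate as a second, clearly labelled line, and give the number of AT patients paced at baseline. State how a change or upgrade of an existing system is treated on that line.

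The cost is one sentence and one extra table row. The case report form should record baseline pacemaker presence for every patient, since section 10 says only that it should be collected. The downside is a slightly smaller denominator, hence a slightly wider interval, and a slightly less favourable leading rate. Nothing already planned is lost.
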